### III. STUDY POPULATION

The study participants will be healthy, low-risk, adult women seeking prenatal care with the Aurora UW faculty midwives and obstetricians at Aurora Sinai Medical Center. This will be a convenience sample of patients who voluntarily present for routine prenatal care, agree to study participation, and are randomized to either waterbirth or conventional land birth. As further research is needed to truly determine our desired sample size for testing our proposed hypotheses, our study aims to determine the feasibility of exploring or testing these hypotheses. This may allow us to make estimations for sample size to plan a larger, randomized controlled study in the future, or to contribute to meta-analyses of waterbirth.

Inclusion criteria based on *A model practice template for hydrotherapy in labor and birth (2016)*:

1. **Prenatal** low-risk, healthy, adult women ( $\geq 18$  years of age), including:
  - a. Able to speak and understand English
  - b. Women with a singleton gestation
  - c. Able to ambulate with no mobility restrictions (i.e., no difficulty getting from seated to standing)
  - d. Less than class III obesity (BMI  $< 40$  kg/m^2) at initiation of prenatal care
  - e. No active infections such as HIV, Hepatitis B, Hepatitis C, HSV outbreak (on prophylaxis acceptable),
    - i. GBS positive is acceptable
  - f. No pre-existing medical conditions such as: heart disease, uncontrolled asthma, diabetes, chronic hypertension, or other condition that requires continuous observation and/or activity restrictions
  - g. No high-risk pregnancy conditions: including preeclampsia, gestational hypertension, preterm gestation, multiple gestation, substance abuse, placental abruption or other unexplained vaginal bleeding, previous cesarean section,

suspected fetal macrosomia (>4500 gm) or intrauterine growth restrictions (<10th percentile), or other condition that requires continuous observation and/or activity restrictions per provider discretion; ultimately patient participation is dependent on provider recommendation

2. **Labor** inclusion criteria:

- h. Greater than 37 weeks and less than 42 completed weeks gestation in vertex presentation
- i. Not hypertensive or febrile (two blood pressures 140/90 four hours apart; two fevers of over 100.4 one hour apart)
- j. Category 1 fetal heart tones (obtained on a 20-minute admission external fetal monitor strip)

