- k. Amniotic sac may be intact or ruptured. If ruptured, amniotic fluid must be clear.

Women will be **excluded** from the study if they do not meet the above inclusion criteria, or they will be further **excluded** under the following circumstances:

- 1. Known need for cesarean section
- 2. Participant may be excluded from the study at any time at the discretion of the birth attendant (reason for study exclusion will be documented but will remain in the study group previously selected based on intention to treat).

Women will be notified of exclusion by their provider, who will also notify appropriate study team members including coordinators. Documentation of exclusion will be done in Epic through a dotphrase (.waterbirthexclusion; Appendix A).

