#### IV. STUDY DESIGN

This study is a pilot randomized control trial that aims to assess feasibility and explore or test (if possible) outcomes of waterbirth to that of conventional land birth for low-risk healthy women and neonates in a hospital setting in Milwaukee, WI. Low-risk healthy adult women will be enrolled from January 2022 through December 2025. The study could be introduced to potentially eligible women in their second trimester. Patient recruitment materials will also be placed in the waiting room and exam rooms. Patient recruitment materials will be created upon receipt of the birthing tub (October 2021) and will be approved by the IRB prior to use. We have attached the recruitment poster for approval.

We plan to enroll women using a random allocation rule in the ratio 2:1, with two women randomized to the waterbirth group for every one woman randomized to the land birth group. Women will be randomized in the Midwifery and Wellness Clinic, Exclusively for Women, and the Women's Health Clinic at Aurora Sinai Medical Center at the beginning of the third trimester (25 weeks 0 days to 34 weeks 0 days gestation) upon consent by the research coordinator, faculty physician(s), or midwives listed on this study. Consent will be documented with a dotphrase (.waterbirthconsent2; Appendix A). Patients will be presented with a sealed envelope which will contain a slip of paper identifying the patient's random assignment to either the waterbirth or land birth (again with a 2:1 randomization allocation). Currently, randomization is completed through REDcap.

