We initially aimed to enroll 120 patients in the study, 80 enrolled within the waterbirth group and 40 in the land group. We recognize that some women will risk-out or opt-out because of the unpredictability of labor and birth. Additionally, we aim to approach most patients eligible for waterbirth with the understanding that some women will not want to participate in a research study. We have recalculated our sample sized based on the current enrollment attrition rate of 39.4% (rate in which patients risk out of the study). With a 2:1 allocation ratio, approximately 120 subjects were initially earmarked to be recruited into the study given 74 would be needed in the waterbirth and 37 would be needed in the land birth group to detect a 40% reduction in epidural use. Following the recommendations of Sakpal, we used the attrition rate (rate in which patients risk out of the study) to calculate adjusted sample sizes as 124 in the waterbirth group and 62 in the land birth group for a total of 186.

Participants who are ineligible for waterbirth will be excluded from both the land or water groups, and no further data will be collected. Please note that given the variable nature of birth, once a woman is randomized and enrolled to either group and meets ongoing eligibility criteria, an intention to treat model will be used for analysis following the birth.

Study participation will be offered to women seeking routine prenatal care in the Midwifery and Wellness Clinic, Exclusively for Women, and the Women's Health Clinic at Aurora Sinai Medical Center at the beginning of the third trimester (25 weeks 0 days to 34 weeks 0 days gestation). Eligible patients will be consented by a research study coordinator (risks and benefits will be done by an Aurora UW Medical Group midwifery or obstetric provider [CNM or physician] listed on this protocol) following the patient's prenatal visit. Note, in rare cases midwifery or obstetric providers listed on this protocol may conduct full consent. Following voluntary consent, all study participants will be randomized (see above for randomization).

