## **VII. DATA COLLECTION**

- » From January 2022 through December 2025 eligible women will be offered study participation during routine prenatal care at 25 weeks 0 days to 34 weeks 0 days gestation. The study could be introduced to potentially eligible women in their second trimester. Several data elements will be reviewed and collected from the delivery record in Epic and the AUWMG midwifery database. REDCap will be utilized for data collection and storage for this study. Data collection will be completed by those listed on this study. After the first year of data collection, we plan to conduct an interim analysis and present year one preliminary data at a scientific meeting (Advocate Aurora Scientific Day 2023).

Variables to be collected at time of consent after coordinators have discussed participating in a randomized control trial:

- Do you wish to voluntarily participate in our randomized control trial that aims to evaluate maternal/neonatal outcomes associated with waterbirths, as well as your satisfaction with the birthing process? (0=No; 1=Yes)

Variables to be collected:

1. *Study related variables*
  - a. Medical reason/s participant becomes ineligible for waterbirth
    - i. Hep C positive (0=No; 1=Yes)
    - ii. Gestational age <37 or >42
    - iii. Non-vertex presentation (0=No; 1=Yes)
    - iv. Hypertensive (0=No; 1=Yes)
    - v. Febrile (0=No; 1=Yes)
    - vi. Category 2 or 3 fetal heart tones (0=No; 1=Yes)
    - vii. Amniotic sac is ruptured and fluid is not clear (0=No; 1=Yes)
    - viii. Other: notes
  - b. Maternal decision to withdraw participation (i.e. desire to leave the water): notes
2. *Maternal variables*
  - a. REDCap Record ID
  - b. Medical record number
  - c. Date of birth
  - d. BMI (kg/m^2) at initiation of prenatal care
    - a. Height (inches) and weight (lbs) at initiation of prenatal care
  - e. Race
  - f. Ethnicity
  - g. Education level
  - h. Marital status
  - i. Gravidity
  - j. Paritya
  - k. Date and time of admission
  - l. Date and time of delivery
  - m. Gestational age at time of delivery (WxDx)
  - n. Maternal position for birth:
    - a. upright (0=No; 1=Yes)
    - b. squatting (0=No; 1=Yes)
    - c. semi-sitting (0=No; 1=Yes)
    - d. left tilt (0=No; 1=Yes)
    - e. right tilt (0=No; 1=Yes)
    - f. hands and knees (0=No; 1=Yes)
    - g. standing (0=No; 1=Yes)
    - h. other (0=No; 1=Yes)
      - i. describe

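### Women who become ineligible for waterbirth after randomisation are dropped with no outcome data, so the planned analysis is not intention-to-treat, and the rule is not reconciled with the exclusion criteria

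*Combined protocol and SAP*

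**What the plan says.** Section IV (Study Design) places randomisation "at the beginning of the third trimester (25 weeks 0 days to 34 weeks 0 days gestation) upon consent". Section III (Study Population) lists labor criteria that can be checked only weeks later: term gestation, vertex presentation, no hypertension or fever, clear fluid if the membranes have ruptured, and "Category 1 fetal heart tones (obtained on a 20-minute admission external fetal monitor strip").

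Three statements govern women who stop qualifying in between:

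- Section IV: "Participants who are ineligible for waterbirth will be excluded from both the land or water groups, and no further data will be collected".
- Section IV, next sentence: "once a woman is randomized and enrolled to either group and meets ongoing eligibility criteria, an intention to treat model will be used for analysis".
- Section III, exclusion 2, on women excluded at any time on the birth attendant's judgement: "reason for study exclusion will be documented but will remain in the study group previously selected based on intention to treat".

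Section VII (Data Collection), item 1a, records "Medical reason/s participant becomes ineligible for waterbirth", with tick-boxes that include hypertension, fever, Category 2 or 3 tracing and non-clear fluid.

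Sections IV and VII (Statistical Plan) cite a "current enrollment attrition rate of 39.4" percent, define it as the rate at which women risk out, and use it to inflate 74 water and 37 land to 124 and 62, a total of 186.

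**The concern.** An intention-to-treat analysis includes every randomised woman in her assigned arm. A rule that applies the term only to women who remain eligible selects on something that happens after randomisation. Whatever the rule is called, the comparison is then between two subsets, and randomisation alone no longer makes them comparable.

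The selection is related to the outcomes. Fever, hypertension, a non-reassuring tracing and non-clear fluid can plausibly precede epidural use, cesarean, a low Apgar score or NICU admission, which are the subject of the primary aim and of Aims 2 and 4. Care is open-label, and eligibility for waterbirth matters in practice mainly in the water arm, so the threshold for declaring a woman ineligible could differ between arms. If it did, the arms would lose different shares of their higher-risk women, and a difference could appear where none exists.

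Stopping data collection also means that the dataset as planned could not support an analysis of all randomised women, even as a check. The pilot is meant to size a larger trial or feed meta-analyses, so any distortion would carry forward.

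**Working it through.** **1. Is removal the working plan?** The sample size shows that it is.

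- Inputs from VII. Statistical Plan: epidural use 59% (land) and 34% (water), 80% power, 0.05 level, one-tailed, 2:1 allocation.
- Pooled formula for the land arm: n = [1.645·√(1.5·p̄(1−p̄)) + 0.842·√(p₁(1−p₁) + p₂(1−p₂)/2)]² / (p₁−p₂)², with p̄ = (0.59 + 2×0.34)/3 = 0.423.
- Numbers: (0.995 + 0.501)² / 0.0625 = 35.8, so 36 land and 72 water. The plan states 37 and 74, so its figure is reproduced to within two women per arm.
- Inflation: 37/(1 − 0.394) = 61.06, rounded up to 62; doubled for 2:1, 124; total 186. This matches the plan.
- Expected loss: 0.394 × 186 = 73.3, or about 49 water and 24 land. About 113 remain (75 and 38), close to the 111 required.

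The calculation works only if the women who risk out are absent from the analysis.

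**2. The two rules side by side.**

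| | Section III, exclusion 2 | Section IV |
|---|---|---|
| Who | Excluded on the attendant's judgement, at any time | Ineligible for waterbirth |
| Analysis | Stays in assigned group | Excluded from both groups |
| Data | Reason documented | None further collected |

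Nothing assigns a given case to one column or the other. Prenatal criterion g in section III also makes participation depend on the provider's recommendation, which blurs the line further.

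**3. How large could the bias be?** This is hypothetical; the documents give neither removal rates by arm nor outcomes among removed women.

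- Assumptions: no true effect; 59% epidural use among all women randomised to each arm; a common epidural rate q among removed women; 39.4% removed overall, split as 42.0% water and 34.2% land. Check: (2×42.0 + 34.2)/3 = 39.4.
- Retained rate in an arm that loses share e: (0.59 − e·q)/(1 − e).
- Retained numbers: 124 × 0.580 ≈ 72 water and 62 × 0.658 ≈ 41 land.
- Rejection: exact binomial probability that the one-tailed 0.05 Pearson test favours water.

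| q | Water retained | Land retained | Spurious benefit of water | Rejection |
|---|---|---|---|---|
| 65% | 0.317/0.580 = 54.7% | 0.3677/0.658 = 55.9% | 1.2 points | about 6% |
| 75% | 0.275/0.580 = 47.4% | 0.3335/0.658 = 50.7% | 3.3 points | about 10% |
| 85% | 0.233/0.580 = 40.2% | 0.2993/0.658 = 45.5% | 5.3 points | about 14% |

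With equal removal (39.4% in each arm) the spurious difference is zero and rejection is about 5%. With q below 59% the sign reverses: at q = 50%, water is 0.380/0.580 = 65.5% and land 0.419/0.658 = 63.7%, which is 1.8 points against water.

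**4. What the corrected analysis does to power.** Suppose women who risk out gain nothing from assignment and share a rate q in both arms. The difference becomes 0.606 × 25 = 15.2 points. At q = 59% the rates are 59.0% and 43.85%. The standard error at 124/62 is 0.0778 under the null and 0.0767 under the alternative, so power = Φ[(0.1515 − 1.645×0.0778)/0.0767] = Φ(0.31), about 62%. At q = 90% it is about 64%. Restoring 80% one-sided power would take about 282 (q = 90%) to 303 (q = 59%) women. If removed women kept the full 25-point effect, power at 124/62 would be about 95%.

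**The case against.** The case for the plan has substance on five points.

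- **The two rules may not collide.** The retention clause is attached only to discretionary exclusions, and section IV's own intention-to-treat sentence is openly conditional. A narrow reading removes criterion failures and keeps discretionary exclusions. This stands: a reader might infer that the rules cannot both be followed, but the text supports only that they are unreconciled. Even on the narrow reading, dropping criterion failures after randomisation is not intention to treat.
- **The conditioning is not on an uncomplicated labor.** A reader might infer that it is. Cesarean, instrumental delivery, shoulder dystocia, hemorrhage and NICU admission are still recorded for retained women, and some listed reasons (hepatitis C, gestational age, presentation) are not labor complications. The condition is continued eligibility for waterbirth, and the documents do not say how much of the 39.4% arises in labor.
- **Differential removal is not shown.** The removal rule names both arms and the criteria are not arm-specific. The second-stage clearance note is for water only, but no text says that withholding it ends data collection. It would go too far to assert that land-arm women are rarely declared ineligible.
- **The loss may be recoverable.** Delivery records are in Epic and reasons are captured, so the documents do not support calling the damage beyond repair.
- **This is a feasibility pilot** that tests hypotheses only if numbers permit. That tempers the weight of the test, but not the need for outcomes on all randomised women.

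**Conclusion.** The point holds. After randomisation, section IV removes women who become ineligible for waterbirth, collects nothing further on them, and uses the term intention to treat for an analysis of those who remain. The sample-size inflation confirms that this is intended. About 73 of 186 randomised women would have no outcomes if the 39.4% rate continues, and section III's retention clause is left unreconciled.

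The size of any bias is unknown. The 1.2 to 5.3 points and the 6% to 14% rejection rest on an assumed split by arm and assumed epidural rates among removed women. A wider gap between arms would enlarge them, equal removal would remove them, and a risk-out epidural rate below 59% would reverse the direction. They show that a modest imbalance matters, not that one exists. Even with equal removal, the result would describe only women who stayed eligible for waterbirth, not all those randomised.

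**What to change.** - In section IV, delete the clause that ends data collection, and reconcile the paragraph with exclusion 2 in section III so that one rule covers every exclusion after randomisation.
- Abstract the delivery-record outcomes from Epic for every randomised woman who has not withdrawn consent, including those who have already risked out where consent allows.
- Make all randomised women, in their assigned arm, the primary analysis set.
- Keep the still-eligible women as a supportive set, defined by the same criteria in both arms.
- Report exclusions by arm and reason.
- Restate the power in VII. Statistical Plan for the analysis of all randomised women, showing the range above.

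The operational cost is an amendment through the IRB and abstraction of records the hospital already holds. The statistical cost is dilution: unless women who risk out share in the effect, 186 women will give less than the stated 80% power. The plan should say so openly; it is not a reason to discard their outcomes.

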## II. SPECIFIC AIMS

The proposed pilot randomized control trial will be approached as a feasibility study to explore or test (if sample size permits) our hypotheses. Additional sample size analyses have been conducted since this study was first submitted as we continue to explore the feasibility of this study in hopes of answering our primary outcome.

**Primary outcome:** Women in the waterbirth group will use less IV narcotic and epidural anesthesia than women in the land birth group.

We further seek to address the following additional specific aims:

**Specific Aim 1:** Evaluate waterbirth outcomes in adult low-risk laboring women randomized to waterbirth in comparison to women randomized to birth on land.

**Hypothesis 1a.** Women in the waterbirth cohort will have shorter labor duration than women in the land cohort.

**Hypothesis 1b.** Women in the waterbirth cohort will be more likely to initiate breastfeeding before discharge.

**Specific Aim 2:** Evaluate the safety of waterbirth in adult low-risk laboring women randomized to waterbirth in comparison to women randomized to birth on land.

**Hypothesis 2a.** Women in the waterbirth cohort will not experience more adverse outcomes (e.g., postpartum hemorrhage, third- or fourth-degree perineal lacerations, etc.) than women in the control group.

**Specific Aim 3:** Evaluate satisfaction with waterbirth in adult low-risk laboring women randomized to waterbirth in comparison to women randomized to birth on land.

**Hypothesis 3.** Women in the waterbirth cohort will experience greater satisfaction scores on the revised United States Birth Satisfaction Scale-Revised (US-BSS-R), than women in the land cohort.

**Specific Aim 4:** Evaluate the safety of waterbirth for term low-risk neonates in comparison to land birth term low-risk neonates.

**Hypothesis 4a.** Infants in the waterbirth group will not experience more adverse outcomes (e.g., NICU admission, APGAR scores <7, umbilical cord injury, etc.) than infants born to women in the land cohort.

**Hypothesis 4b.** Infants in the waterbirth group will experience fewer instrumental (e.g., forceps, vacuum, etc.) or cesarean deliveries.

**Hypothesis 4c.** Infants born to women in the waterbirth cohort will have immediate skin-to-skin contact.

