Data collection will be completed as described below and will be obtained from Epic and the AUWMG midwifery database. A validated questionnaire *The US Birth Satisfaction Scale Revised* (US-BSS-R) will be used to evaluate maternal satisfaction and will be obtained within the first three days postpartum by either a study coordinator or midwife provider via an iPad. In some cases, the US-BSS-R will be collected by phone. We have obtained permission from the authors to use the validated scale US-BSS-R. The US-BSS-R is the recommended birth satisfaction measure by the International Consortium for Health Outcomes Measurement (ICHOM). Questions (below) are measured on 5-point Likert scale [strongly agree-strongly disagree] and a full copy of the scale was obtained from the authors and is available upon request:

1. I came through childbirth virtually unharmed.
2. I thought my labor was excessively long.
3. The delivery room staff encouraged me to make decisions about how I wanted my birth to progress.
4. I felt very anxious during my labor and birth.
5. I felt well supported by staff during my labor and birth.
6. The staff communicated well with me during labor.
7. I found giving birth a distressing experience.
8. I felt out of control during my birth experience.

9. I was not distressed at all during labor.
10. The delivery room was clean and hygienic

Routine management of the tub will be done in compliance with Infection Control and facility services. Water temperature will be maintained at less than or equal to 100 degrees Fahrenheit and will be monitored and recorded hourly through both a paper copy that will go the mid-wife call room (or study binder), as well as through an EPIC smart phrase .waterbirthlaborprogressnote (Appendix A and Appendix B). The Water Tub Protocol (Appendix C) has been created following receipt of the tub.

Waterbirths are an alternative method of pain control and are not standard of care. Therefore, only patients who voluntarily agree to participate in this study will be able to undergo waterbirth. We will collect regularly recorded measures, in addition to patient satisfaction surveys for all participants. The US-BSS-R questionnaire is the only deviations from standard care for patients in the conventional land birth group.

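### Satisfaction survey (Hypothesis 3): a midwife who gave the birth care may collect it, collector and mode are not recorded, and a difference could not be credited to immersion alone

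*Combined protocol and SAP*

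**What the plan says.** Hypothesis 3 (II. Specific Aims) is directional: "Women in the waterbirth cohort will experience greater satisfaction scores". VII. Statistical Plan sets a one-tailed 0.05 criterion.

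IV. Study Design says the US-BSS-R "will be obtained within the first three days postpartum by either a study coordinator or midwife provider via an iPad". It adds: "In some cases, the US-BSS-R will be collected by phone". No rule says which collector is used for whom, or which cases go to phone. No blinding of the collector is described.

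The same section prints the ten items. Item 3 reads "The delivery room staff encouraged me to make decisions about how I wanted my birth to progress", item 5 reads "I felt well supported by staff during my labor and birth", and item 6 asks how well staff communicated during labor.

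On access, IV. Study Design states that "only patients who voluntarily agree to participate in this study will be able to undergo waterbirth". Women are randomized 2:1 at 25 to 34 weeks and see their assignment then.

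The one variable listed at consent (VII. Data Collection) is yes or no to a question that begins "Do you wish to voluntarily participate in our randomized control trial that aims to evaluate maternal/neonatal outcomes associated with waterbirths". No item on preferred birth appears in the list. For the survey, item v of the maternal variables records the score and the postpartum day of completion, and nothing on who collected it or how.

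**The concern.** Two features bear on one unblinded, self-reported outcome.

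The first is collection. A woman asked by a midwife to rate staff support may answer more kindly than one asked by a coordinator, and more so if that midwife cared for her in labor. A phone interview may also draw different answers from an iPad. If collector or mode differed by arm, part of the satisfaction contrast would come from the way it was measured. With neither recorded, the analyst could not tell.

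The second is what the contrast means. Some women will have joined because the trial is the only way to a waterbirth. Randomization balances that preference between arms, but not the consequence of knowing the allocation. A woman who wanted water and drew land knows it for weeks before she answers. Any effect of getting or missing the wanted arm is part of the difference, and the data cannot separate it from the effect of the water.

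Satisfaction is one of the three purposes named for the pilot in I. Background and Significance, and the results are meant to inform a larger multi-center trial, which could inherit both features.

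**Working it through.** **1. Plan's own figures.** The documents give no sample size, effect size or standard deviation for satisfaction. The numbers of women come from the epidural calculation: 59% against 34%, 2:1, 80% power. One-sided, without continuity correction, with pooled proportion (0.59 + 2 × 0.34)/3 = 0.4233:

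n(land) = [1.645 × √(1.5 × 0.4233 × 0.5767) + 0.8416 × √(0.59 × 0.41 + 0.34 × 0.66/2)]² / 0.25² = (0.995 + 0.501)² / 0.0625 ≈ 35.8, so 36 land and 72 water.

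The plan states 37 and 74, which is close. The inflation also reproduces: 37/(1 − 0.394) = 61.06, rounded up to 62; 2 × 62 = 124; total 186. I use 74/37 and 124/62 below only as group sizes.

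**2. Collector.** Let p_W and p_L be the shares of surveys collected by a midwife in each arm, and c the effect of midwife collection on the score. If c is the same in both arms:

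shift in (water − land) = c × (p_W − p_L)

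This is zero when p_W = p_L. From the documents: three of ten items rate staff. Assumed: items score 0 to 4, and midwife collection raises each staff item by one category, so c = 3 × 1 = 3 points on a 0 to 40 scale. If the shares differ by 10 to 50 percentage points in either direction, the shift is ±(3 × 0.10) to ±(3 × 0.50), or ±0.3 to ±1.5 points. Its sign is the sign of p_W − p_L, on which the documents are silent.

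**3. Getting or missing the wanted arm.** Let q be the share of enrollees who prefer water, d the score lost by missing it, and m the share of water-preferring women in the water arm who also miss it and stay in the analysis:

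contribution to (water − land) = q × d × (1 − m)

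Assume q = 0.80 and d = 1 to 3 points. With m = 0 this is 0.8 to 2.4 points; with m = 0.5 it is 0.4 to 1.2 points. None of q, d or m is given. This is part of the assignment effect, not an error in it; the issue is only how it is interpreted.

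**4. What a shift would do to the test.** With no true effect and a spurious shift of b standard deviations towards water:

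P(significant) = Φ(b/SE − 1.645), SE = √(1/n_W + 1/n_L)

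SE = 0.201 for 74/37 and 0.156 for 124/62.

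| b (SD) | 74/37 | 124/62 |
|---|---|---|
| 0 | 5% | 5% |
| 0.1 | 12.5% | 15.8% |
| 0.2 | 25.7% | 36.0% |
| 0.3 | 43.8% | 61.2% |

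A shift the other way hides an effect instead. At b = −0.2 and 74/37, Φ(−0.993 − 1.645) = 0.4%. For scale, the smallest true difference detectable with 80% power is (1.645 + 0.842) × SE = 0.50 SD at 74/37 and 0.39 SD at 124/62.

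Without a standard deviation, the points in steps 2 and 3 cannot be placed in this table. It shows only that modest shifts matter at these sizes.

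**The case against.** The strongest reply has four parts.

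- **Randomization protects the comparison.** Preference is balanced in expectation, so a self-selected sample mainly limits generalizability. A reader might infer that no satisfaction difference could be credited to waterbirth at all. The documents do not support that: the contrast still estimates the effect of assignment in women willing to enrol. What stands is narrower, that it cannot be credited to immersion alone.
- **The documents do not say that women are surveyed by the midwives they are rating.** The items speak of staff, not midwives; nothing says the collector attended the birth; and iPad entry may already be self-completion. This is correct. What stands is that the plan does not rule it out.
- **Direction is not shown.** A reader might infer that both features push towards Hypothesis 3. Coordinators and midwives may collect in either arm, so equal courtesy cancels. Women assigned water who leave the tub can also be disappointed, and where they stay in the intention-to-treat analysis they lower the water score. That most enrollees prefer water is itself an inference. This part of the reply stands in full.
- **The stakes are limited.** Satisfaction is a secondary aim of a pilot, no sample size rests on it, and immersion cannot be blinded. This stands too, and sets the severity.

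Consent pages are not in the documents, so a preference question there cannot be excluded; the listed variables contain none.

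**Conclusion.** A minor point that holds. The plan lets a midwife provider obtain a scale that partly rates staff, does not exclude those who gave the birth care, and records neither collector nor mode. An imbalance between arms in either could not be detected or handled, and its direction is unknown. Separately, a satisfaction difference should be read as the effect of assignment to waterbirth among women willing to enrol.

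These conclusions rest on the text. The sizes do not: apart from the item count and the planned group sizes, every input to the illustrations is assumed. They show that a shift of 0.2 to 0.3 SD would matter at 74/37, not that one of that size will occur.

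**What to change.** 1. **IV. Study Design, questionnaire paragraph.** State that the woman completes the US-BSS-R herself on the iPad, handed over by the study coordinator, or by phone with the coordinator if none is on site. Bar anyone who gave her labor or birth care from collecting it.
2. **VII. Data Collection, maternal satisfaction item.** Add two fields, collector and mode (iPad or phone), and report both by arm.
3. **Hypothesis 3 conclusion.** Word it as the effect of assignment to waterbirth among women willing to enrol.
4. **Optional.** For remaining enrollees, ask preferred birth (water, land or none) at consent, before allocation is revealed, and use it descriptively only. Enrolment is under way, women already enrolled cannot supply it, and the land arm is small, so subgroup results by preference would carry little weight.

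Cost: protocol wording and two REDCap fields, using coordinators who already collect the survey. The downside is a few more phone surveys, which the mode field would make visible.
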